7.2.2.4.1 Hematology

Hematology tests are to be performed by the central laboratory according to the schedule of assessments and collection plan outlined respectively in [Table 7-1a](#), [Table 7-1b](#), [Table 7-2](#), and [Table 7-4](#).

7.2.2.4.2 Clinical chemistry

Chemistry tests are to be performed by the central laboratory according to the schedule of assessments and collection plan outlined respectively in [Table 7-1a](#), [Table 7-1b](#), [Table 7-2](#), and [Table 7-4](#).

7.2.2.4.3 Urinalysis

Urinalysis tests are to be performed according to the schedule of assessments and collection plan outlined respectively in [Table 7-1a](#), [Table 7-1b](#), [Table 7-2](#), and [Table 7-4](#).

A midstream urine sample (approx. 30 mL) will be obtained, in order to avoid contamination with epithelial cells and sediments, and allow proper assessments.

A semi-quantitative "dipstick" evaluation will be performed.

7.2.2.4.4 Coagulation

Coagulation factors specified in [Table 7-4](#) will be assessed by the central laboratory according to [Table 7-1a](#), [Table 7-1b](#) and [Table 7-2](#).

7.2.2.4.5 Thyroid Panel

Thyroid Panel specified in [Table 7-4](#) will be assessed by the central laboratory according to [Table 7-1a](#), [Table 7-1b](#) and [Table 7-2](#).

7.2.2.4.6 Additional hormones

Additional hormones as specified in [Table 7-4](#) will be assessed by the central laboratory according to [Table 7-1a](#), [Table 7-1b](#) and [Table 7-2](#).

7.2.2.4.7 Other laboratory parameters

Other laboratory parameters as specified in [Table 7-4](#) will be assessed by the central laboratory according to [Table 7-1a](#), [Table 7-1b](#) and [Table 7-2](#).

7.2.2.4.8 Pregnancy and assessments of fertility

Serum pregnancy tests will be performed at screening and End of Treatment, and analyzed by the central laboratory. Urine dipstick pregnancy testing will be performed on site as indicated in [Table 7-1a](#), [Table 7-1b](#) and [Table 7-2](#).

If a urine pregnancy test is performed and is found to be positive, this will require immediate interruption of study drug until serum β -hCG is performed and found to be negative. If positive, the patient must be discontinued from the trial.

When performed at screening, the result of this test must be received before the patient may be randomized.

7.2.2.5 Radiological examinations

Table 7-5 Imaging Assessment collection plan

Procedure	Screening	During Treatment/Extension
Pituitary MRI (or CT)	Mandated at screening	Mandated, approximately every 6 months

Pituitary MRI scanning with gadolinium enhancement will be performed at visits according to [Table 7-1a](#), [Table 7-1b](#), [Table 7-2](#), and [Table 7-5](#). These will be assessed centrally by the imaging vendor to screen for pituitary enlargement either by tumor volume or maximum

dimension of tumor. If MRI scan with intravenous contrast (gadolinium) is contraindicated for a patient, then a non-contrast MRI scan should be performed. If the MRI cannot be performed at all, then a CT of the pituitary (with i.v. contrast if not contraindicated) may be performed. Regardless of imaging type, all regularly scheduled pituitary imaging will be centrally reviewed for consistency in the measurement of dimensions. The modality should remain consistent to that used at baseline unless there is a development of a contraindication. Please see the study imaging manual for further information. If EOT occurs less than 6 months before the scheduled Week 96 visit, MRI (or CT) and DXA is not mandatory at EOT.

7.2.2.6 Cardiac assessments

Cardiac monitoring will include 12-lead Safety ECGs, which are the primary assessment of safety at study visits. The 24 hour Holter assessments are not intended to provide real-time assessment of cardiac intervals and cardiac rhythm.

Table 7-6 ECG collection plan

Week	Day	Time point	ECG Type	Central or Local reading reading
Post wash-out (up to Week -3)	up to -15	Anytime	12 Lead	Local
-2 to -1	-14 to -1	Anytime	12 Lead	Local
-2 to -1	-14 to -1		24-hour Holter	Central
1	1	Pre-dose	12 Lead	Local
1, 2, 5, 8, 12, 14, 17, 20, 23, 26, 29, 32, 36, 40, 44	1, 15, 36, 57, 85, 99, 120, 141, 162, 183, 204, 225, 253, 281, 309	1.5 hours Post-dose	12 Lead	Local
48*	337*	Anytime for patients not continuing in extension	12 Lead	Local
2, 12, 14, 36	15, 85, 99, 253	Start at Pre-dose	24-hour Holter	Central
Post Treatment Follow-up week 2, 5, 8, 12**	15, 36, 57, 85**	Anytime	12 Lead	Local
Post Treatment Follow-up week 2, 12**	15, 85**	Anytime	24-hour Holter	Central
Optional Extension: 48*, 60, 72, 84, 96 and every six month afterward ***	337*, 421, 505, 589	1.5 hours Post-dose	12 Lead	Local
End of treatment extension visit		Anytime	12 Lead	Local
Optional Extension: 72	505	Start at Pre-dose	24-hour Holter	Central
End of treatment extension visit****			24-hour Holter	Central
Post Treatment Follow-up	Last dose + 30d	Anytime	12 Lead	Local
Unscheduled assessment		Anytime	12 Lead	Local

Week	Day	Time point	ECG Type	Central or Local reading reading

*Patients will have only one ECG at Week 48 (Day 337). For patients not continuing in optional extension, ECG will be performed anytime during the visit. For patients continuing in optional extension, ECG will be performed at 1.5 hours post-dose, except for EOT Ext., if applicable
 
**For patients who discontinued study drug during Period 1.
 
***The patients who have completed Week 96 prior to the completion of study will be followed every six months as per the schedule of assessments in Table 7-2 until transitioning either to a separate long-term safety follow-up study, a local alternative treatment option, or the completion of the study, whichever occurs first.
 
****End of treatment optional Extension visit assessment should be completed at the time the patients are transitioning either to a separate long-term safety follow-up study, a local alternative treatment option, or the completion of the study, whichever occurs first. Note: Patients end participation in the optional extension period study within 4 weeks after Protocol Amendment 02 approval at the site, or by Week 96, whichever occurs first.
				

7.2.2.6.1 24-hour Holter Electrocardiogram

Twenty-four hour continuous 12-lead Holter recording with central reading of data are done on each patient according to the [Table 7-1a](#), [Table 7-1b](#), [Table 7-2](#), and [Table 7-6](#). Patients should be instructed to return their 24-hour Holter flashcards to the site at their next study visit in order to facilitate timely central reading of the Holter data.

7.2.2.6.2 Electrocardiogram (ECG)

Twelve-lead safety ECGs are collected at the study sites according to [Table 7-1a](#), [Table 7-1b](#), [Table 7-2](#), and [Table 7-6](#). At each visit when a study drug dose is administered, the safety ECG should be collected at 1.5 hours post-dose (approximately at the time of C_{max}).

Twelve-lead safety ECGs are collected at the study site using ECG equipment provided by or validated by vendor. This ECG must be read on site by a qualified physician (e.g., the investigator, or another qualified physician such as a consulting cardiologist) at the time they are collected and documented on the ECG eCRF.

Each 12-lead Safety ECG tracing must be labeled with the:

- study number
- patient initials
- patient number
- date and time

and kept in the source documents at the study site. The clock on the ECG machine must be synchronized with the central clock on a daily basis.

Record the following on the eCRF:

- date and time of ECG
- heart rate
- PR interval
- QT and QTcF interval
- QRS duration

The Fridericia QT formula (QTcF) to correct for variations in heart rate must be used for clinical decisions.

The purpose of the safety ECG is to identify patients with clinically significant ECG abnormalities. On the day of the first study drug administration (Day 1), pre-dose ECGs must be done in triplicate. The mean of the QTcF from these 3 tracings is used as the baseline QTcF to be compared with subsequent ECGs.

ECGs with clinically significant abnormalities must be reported on the ECG eCRF. The overall interpretation will be collected with a Yes/No statement to confirm if any clinically significant abnormalities are present which need to be specified further.

A “notable ECG abnormality” is defined as:

- Day 1 only: an increase in QTcF > 30 msec at 1.5 hours post-dose, compared to the mean pre-dose baseline QTcF from the same day
- QTcF > 480 msec with acute cardiovascular risk, as assessed by a consulting cardiologist
- Any QTcF > 500 msec, confirmed by a consulting cardiologist
- QTcF increase > 60 msec from baseline.

Notable ECG abnormalities must be recorded on the Adverse Events eCRF page. If there is a notable abnormality, then a cardiology consult should be obtained as soon as possible, and the Novartis Medical Monitor for this trial notified of the event.

For any ECGs with clinically significant or notable ECG abnormalities, two additional 12-lead ECGs should be performed to confirm the safety finding and the triplicate ECGs collected should be transferred for central review.

ECGs must be recorded after 10 minutes rest in the supine position to ensure a stable assessment.

The preferred sequence of cardiovascular data collection during study visits is ECG collection first, followed by vital signs, and then blood sampling for osilodrostat pharmacokinetic (PK) assessment (Figure 7-1). ECG procedure may also be performed 30 minutes after PK sampling.

Figure 7-1 Sequence of cardiovascular data collection

Original ECG tracings, appropriately signed, will be archived at study site.

7.2.2.7 QT monitoring

[figure not shown]
QT monitoring will occur as follows:

- On the first day of the first administration of osilodrostat (Day 1), pre-dose baseline ECGs must be done in triplicate. The mean of the QTcF values from these three ECG tracings is used to determine the mean baseline QTcF.
- On Day 1, if the safety ECG (1.5 hours post-first dose of osilodrostat) shows an increase in QTcF > 30 msec from the mean baseline value, or the QTcF is > 480 msec, then the patient must be discontinued from study. The ECG reading should be performed in triplicate (to determine a mean value) and reviewed promptly by a consulting cardiologist before discontinuing the patient from osilodrostat therapy.
- If at any following visit, a QTcF > 480 msec is observed or an increase of the QTcF of > 60 msec compared to baseline mean QTcF assessment, then two additional ECGs, each 2-3 minutes apart, need to be taken after the initial ECG. The mean QTcF from the triplicate ECGs will be determined. If the mean QTcF is > 480 msec or the mean QTcF increase is > 60 msec compared to baseline, the patient has to interrupt study drug while an urgent cardiology consultation is obtained to re-evaluate the ECG and perform a clinical consultation. If immediate treatment is required for patient safety, this should be initiated at the study site without delay and without waiting for confirmation by a cardiologist.

Based on the cardiologist consultation, the following should occur:

- If a mean QTcF > 480 msec is NOT confirmed, no further action needs to be taken.
- If the cardiologist confirms a mean QTcF > 500 msec, the patient has to discontinue according to the discontinuation procedure described in [Section 7.1.4](#). and an unscheduled PK sample is to be collected. The patient must remain under observation until the QTcF is < 480 msec and serum electrolytes, calcium, and magnesium are measured and the results normal. This observation may be done at the site, in an Emergency Room, or a cardiology clinic, as appropriate and depending upon local resources.
- If the cardiologist confirms that QTcF > 480 msec, osilodrostat treatment is temporarily interrupted and a thorough evaluation is performed to assess the patient for acute cardiovascular risk, and for possible underlying heart disease that needs additional evaluation and management. In addition, an unscheduled PK sample will be collected.
 - If based upon the assessment by the cardiologist, the investigator considers that there is an acute cardiovascular safety risk and that the subject should not continue with study medication, the subject needs to be discontinued immediately (discontinuation criteria described in [Section 7.1.4](#)).
 - If based upon the assessment by the cardiologist, the investigator considers that there is not an acute cardiovascular safety risk; the subject can continue to receive study medication.

Figure 7-2 QT Monitoring Flow Chart

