2.2.6 ECG Monitoring

Cardiac monitoring will include 12-lead Safety ECGs at pre-dose (Day 1) and 1.5 hours post-dose at each visit the patient receives study drug. The Safety ECGs are the primary cardiac safety assessment, and their rationale is to assess the maximum change in QTcF in each individual patient each time they receive study drug at the site. The 12-lead safety ECGs are read in real-time on-site by the PI or other qualified physician (e.g., cardiologist), and if there is QT prolongation (QTcF > 480 ms or increase > 60 ms from baseline assessment), patients are to be managed according to the QT Monitoring Flow Chart in [Figure 7-2](#).

In addition, 24-hour continuous 12-lead Holter recordings will be performed at baseline, Weeks 2, 12, 14, 36, and as applicable at Week 72 and at the end of treatment visit in the optional Extension phase. The 24 hour Holter assessments are not intended to provide real-time assessment of cardiac intervals and cardiac rhythm; the recordings are read centrally.

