6.1.1 Dosing regimen

Study drug should be taken twice a day (b.i.d.). For example a patient on a 2 mg b.i.d. dose will take 2 mg in the morning and 2 mg in the evening, providing a total daily dose of 4 mg. Study drug should be taken at approximately the same time each day, with about 12 hours between each dose administration. Osilodrostat can be dosed without regard to food. The patient will maintain a diary of each drug self-administration in order to track compliance. If vomiting occurs during the course of treatment, patients should not take the study drug again before the next scheduled dose. Patients should be instructed not to make up missed doses. A missed dose is defined as a case when the dose is not taken within 4 hours after the usual dosing time.

On study visit days, patients should be reminded not to take the study drug prior to the site visit to ensure compliance with the ECG and pre-dose PK sampling procedure. The morning dose of study drug on the visit days should be administered at the site after the ECG and pre-dose PK sampling has been completed.

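### Section 7.2.2.7 interrupts drug for a confirmed QTcF rise above 60 msec, but its outcome rules use absolute QTcF only, so a rise that stays at or below 480 msec ends in no action

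*Protocol*

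**What the plan says.** For visits after Day 1, Protocol 7.2.2.7 has two triggers joined by *or*. One is a triplicate-mean QTcF above 480 msec; for the other, "or the mean QTcF increase is > 60 msec compared to baseline, the patient has to interrupt study drug". Either one leads to an urgent cardiology consultation.

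Three outcomes follow, each defined by absolute QTcF:

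- Not confirmed above 480: "If a mean QTcF > 480 msec is NOT confirmed, no further action needs to be taken".
- Confirmed above 500: discontinue, with an unscheduled PK sample and observation.
- Confirmed above 480: temporary interruption, an unscheduled PK sample, and "a thorough evaluation is performed to assess the patient for acute cardiovascular risk, and for possible underlying heart disease".

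Two further bullets give the decision to stop or continue. The second says that if "the investigator considers that there is not an acute cardiovascular safety risk; the subject can continue to receive study medication". Neither carries a QTcF threshold, and the extracted layout does not settle whether they sit under the above-480 branch or stand alone.

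Elsewhere the protocol treats the rise as important in its own right. Section 2.2.6 calls for management by Figure 7-2 "if there is QT prolongation (QTcF > 480 ms or increase > 60 ms from baseline assessment". Section 7.2.2.6.2 lists a rise above 60 msec from baseline as a notable abnormality with no absolute floor. Section 7.1.4 requires discontinuation for a rise above 60 msec, but measured against the pre-dose reading at the same visit.

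**The concern.** One arm of the trigger has no matching outcome. A patient whose confirmed mean goes from 400 to 465 msec has drug interrupted, sees a cardiologist, and then meets the first outcome rule, because 480 was not exceeded. If that rule is instead read as applying only to patients triggered by the 480 limit, this patient has no threshold-based outcome at all. Either reading leaves a defect.

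The result is also out of line with neighbouring rules. On Day 1 a rise above 30 msec alone ends treatment. A 65 msec rise against a same-visit pre-dose ECG means stop, while the same 65 msec against study baseline means nothing further. Day 1 tests only 2 mg; doses can later reach 30 mg b.i.d., where the defective rule governs.

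At stake are the mandated evaluation for acute cardiovascular risk and underlying heart disease, and the unscheduled PK sample (still required under 7.2.3 if the event ends treatment). If the two stop/continue bullets are nested under the above-480 branch, the written decision on restarting is lost too.

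**Working it through.** **1. Where the gap lies.** A triggered patient ends in no action when

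60 < rise ≤ 480 − baseline,

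which is non-empty only if baseline < 420 msec. Entry limits (5.3) allow up to 450 msec in men and 460 in women.

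| Baseline QTcF (msec) | 480 − baseline | Rises in the gap (msec) |
|---|---|---|
| 360 | 120 | 60–120 |
| 388.6 | 91.4 | 60–91.4 |
| 400 | 80 | 60–80 |
| 410 | 70 | 60–70 |
| 420 | 60 | none |

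The 388.6 row is the phase II screening mean (8.1.3.1; SD 62.80), so baselines in this range are to be expected.

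As a logic check, every pair of baseline (340 to 450 msec) and on-treatment QTcF (up to 540 msec) was listed in 1-msec steps. Of 9,900 triggered pairs, 3,240 end in no action, all with a rise above 60 and a baseline below 420. These are counts of rule outcomes, not probabilities.

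**2. Does the 7.1.4 same-visit rule close it?** It needs a pre-dose ECG at the visit, and the documents disagree on whether there is one.

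- Section 2.2.6 lists "12-lead Safety ECGs at pre-dose (Day 1) and 1.5 hours post-dose at each visit the patient receives study drug", and Table 7-6 agrees: pre-dose on Day 1 only.
- Section 6.1.1 says the visit-day dose "should be administered at the site after the ECG and pre-dose PK sampling has been completed", which suggests a pre-dose ECG.
- Holters start pre-dose at Weeks 2, 12, 14 and 36, but "The 24 hour Holter assessments are not intended to provide real-time assessment of cardiac intervals and cardiac rhythm".

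With no pre-dose ECG after Day 1, the whole window in step 1 is open.

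**3. If a pre-dose ECG is taken.** Assume a QTcF effect proportional to concentration, single-exponential decline, and a half-life t of 3–5 h (1.2.1.2.1). The predictions in 1.2.1.2.4 roughly support proportionality: 4.1/174 = 0.0236 and 6.3/284 = 0.0222 ms per ng/mL.

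From 1.5 h after one dose to the next pre-dose ECG is 12 − 1.5 = 10.5 h. The fraction of effect remaining is f = 0.5^(10.5/t). The same-visit rise is (1 − f) × rise from baseline, so it exceeds 60 only when the rise from baseline exceeds 60/(1 − f).

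| Half-life | f | 60/(1 − f) | Still open, baseline ≤ 400 | Still open, baseline 410 |
|---|---|---|---|---|
| 3 h | 0.088 | 65.8 msec | 60–65.8 | 60–65.8 |
| 5 h | 0.233 | 78.3 msec | 60–78.3 | 60–70 (all) |

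A rise already present before the dose, and not tied to dose timing, escapes the same-visit rule entirely. Hypokalemia is one route: 5.3 lists it as a QTc risk factor and 2.6 as a potential effect of osilodrostat.

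**4. Does scheduled PK replace the lost sample?** Core visits after Day 1 with a 1.5 h ECG (Table 7-6) are Weeks 2, 5, 8, 12, 14, 17, 20, 23, 26, 29, 32, 36, 40 and 44, which is 14. Table 7-7 has a 1–2 h sample at the first 10. Weeks 32, 36, 40 and 44 have none.

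**The case against.** The strongest point is Figure 7-2. Section 2.2.6 sends both triggers to that flow chart, and it is not visible in the public text. It may contain the missing branch, in which case the text is an incomplete summary rather than the only rule. The nesting of the two stop/continue bullets is also unreadable; if they stand alone, they already cover this patient. Both limits stand. Neither rescues the sentence: with a complete figure or free-standing bullets, an instruction to do nothing more would contradict them.

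The patient is far from unprotected. Interruption and cardiology consultation have already happened. AE entry, Medical Monitor notification and central review follow under 7.2.2.6.2. The investigator must stop drug if continuing would be detrimental (7.1.4) and may order any testing in a major safety issue (6.3.1). One can also read the interruption as lasting only for the consultation. All this lowers the practical risk, but none of it states what happens to study drug after a confirmed rise.

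The hypokalemia route is also controlled: supplementation is suggested at 3.3 mEq/L or below (6.1.3), Table 6-1 covers interruption and replacement, and 7.1.4 requires stopping at confirmed values below 2.8 mmol/L, or below 3.0 if persistent. These controls reduce the chance of such a rise; they do not supply the missing ECG outcome.

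Finally, the event should be rare. The predicted maximum mean effect at 30 mg is 6.3 ms. In the thorough QT study no subject rose more than 60 ms, even with a 150 mg arm whose maximum mean effect was 25.4 ms. That stands, although those were healthy volunteers.

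**Conclusion.** The concern holds for the text of 7.2.2.7: the outcome rules do not match the triggers. The gap affects patients with baseline QTcF below 420 msec and rises above 60 msec up to 480 minus baseline. With no pre-dose ECG after Day 1, the whole window is open. With one, a drug-driven rise of 60 to about 66 msec (3 h half-life) or 78 msec (5 h) stays open at baseline 400 or below, under the proportional-effect assumption. A rise unrelated to dose timing stays fully open.

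The documents give no expected number of such events, and it should be small. The efficacy analyses are unaffected. The correction is still worth making, because a cardiac stopping algorithm should give a defined outcome for each trigger it sets. The finding does not extend to Figure 7-2.

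**What to change.** Reword the first outcome along these lines: *when neither a mean QTcF above 480 msec nor a mean rise above 60 msec from baseline is confirmed, nothing more is required.* Add a confirmed mean rise above 60 msec to the existing interrupt-and-evaluate branch, with its stop/continue decision and unscheduled PK sample. Leave the above-500 rule and the 7.1.4 same-visit rule as they are; the latter takes precedence where a pre-dose ECG exists. Make the text and Figure 7-2 agree.

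On the grid used above, this moves all 3,240 gap pairs to evaluation (2,220 + 3,240 = 5,460) and leaves the 4,440 discontinuation pairs unchanged.

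The cost is one or two sentences, plus an occasional extra cardiovascular evaluation and PK sample, both already in use for QTcF above 480 msec.

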7.2.3 Pharmacokinetics

Blood samples for osilodrostat pharmacokinetic (PK) evaluation will be collected from all patients who receive at least one dose of study drug. Pharmacokinetic blood sampling will be performed in each study period as indicated in the Visit Evaluation Schedule (Table 7-1a, Table 7-1b and Table 7-2). Time points of blood sample collection for PK analyses are outlined in Table 7-7.

All ECG procedures should be taken prior to and/or 30 minutes after any PK blood draws since sampling for PK impacts ECG measurements. Complete dosing information, including the date and time of actual blood draw and time of the last study drug dose prior to the sampling (24-h

clock time), must be obtained on all sampling days and recorded on the PK eCRF and/or Contract Research Organization (CRO) requisition form(s). Sampling problems will be noted in the relevant field in the eCRF.

An additional blood sample (unscheduled) should be collected in the event that a patient experiences an AE which requires premature termination from the study drug.

